Grade 2 Requires infusion interruption but responds promptly to symptomatic treatment (e.g., antihistamines, NSAIDS, narcotics, IV fluids); prophylactic medications indicated for < =24 hrs	
Stop Infusion and monitor symptoms. Additional appropriate medical therapy may include but is not limited to:
 
 IV fluids Antihistamines NSAIDS Acetaminophen Narcotics 
Increase monitoring of vital signs as medically indicated until the subject is deemed medically stable in the opinion of the investigator.
 
If symptoms resolve within one hour of stopping drug infusion, the infusion may be restarted at 50% of the original infusion rate (e.g. from 100 mL/hr to 50 mL/hr). Otherwise dosing will be held until symptoms resolve and the subject should be premedicated for the next scheduled dose.
 
Subjects who develop Grade 2 toxicity despite adequate premedication should be permanently discontinued from
	
Subject may be premedicated 1.5h (\pm 30 minutes) prior to infusion of MK-3475 with:
 
Diphenhydramine 50 mg po (or equivalent dose of antihistamine).
 
Acetaminophen 500-1000 mg po (or equivalent dose of antipyretic).

NCI CTCAE Grade	Treatment	Premedication at subsequent dosing
further trial treatment administration.		
Grades 3 or 4 Grade 3: Prolonged (i.e., not rapidly responsive to symptomatic medication and/or brief interruption of infusion); recurrence of symptoms following initial improvement; hospitalization indicated for other clinical sequelae (e.g., renal impairment, pulmonary infiltrates) Grade 4: Life-threatening; pressor or ventilatory support indicated	Stop Infusion. Additional appropriate medical therapy may include but is not limited to: IV fluids Antihistamines NSAIDS Acetaminophen Narcotics Oxygen Pressors Corticosteroids Epinephrine Increase monitoring of vital signs as medically indicated until the subject is deemed medically stable in the opinion of the investigator. Hospitalization may be indicated. Subject is permanently discontinued from further trial treatment administration.	No subsequent dosing

Appropriate resuscitation equipment should be available in the room and a physician readily available during the period of drug administration.
 
For Further information, please refer to the Common Terminology Criteria for Adverse Events v4.0 (CTCAE) at http://ctep.cancer.gov
		

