No other SBRT dose modification for individual patients is permitted during the phase Ib portion of the study. During the phase 2a portion, at the discretion of the treating radiation oncologist and with the agreement of the principal investigator, the prescription dose for SBRT may be reduced in an effort to reduce the risk of toxicity. In this case, one of the 3 dose levels specified in the dose escalation section 5.3 will be used.

Adverse events that occur during or after SBRT should be managed per section 5.5, or with best supportive care.

53 SBRT Dose-Escalation or De-Escalation

In the Phase 1b (SBRT dose escalation/de-escalation) portion, patients will be allocated to Arm A (Lung) or Arm B (non-Lung) based on the anatomic site of the target chosen for SBRT. Dose escalation or de-escalation will be done separately for each arm, and the MTD determined separately for each arm. Once an MTD has been determined for lung and non-lung targets, future patients with those SBRT targets will be allocated to the Phase IIa portion of the trial.

In the Phase 2a (expansion) portion, patients will be treated at the SBRT MTD for lung or non-lung lesions, as appropriate.

Dose-Escalation or De-Escalation

In the Phase Ib portion of the trial, the SBRT dose will be escalated or de-escalated in successive cohorts. The starting dose will be 3000 cGy in 5 fractions. A single de-escalation cohort (1000 cGy in a single fraction), and a single escalation cohort (3000 cGy in 3 fractions) will be allowed.

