Because SBRT target selection and treatment will occur in a rolling fashion after a patient progresses on the pre-SBRT MK-3475, availability for enrollment on the dose escalation cohorts will be somewhat unpredictable. In an effort to maximize the number of available treatment slots, enrollment in the dose escalation arms will be done using a “Rolling Six” design, following the guidelines in Table 5, below[56]. A minimum of two patients will be enrolled at each dose level. After 2 patients have been enrolled, the treatment cohort will be determined by the number of patients enrolled, the number who have experienced a DLT, the number who have not, and the number who have not yet completed the DLT follow-up period. The rolling enrollment design allows more than three patients to be enrolled within a dose cohort before safety has been demonstrated, and reflects the fact that both MK-3475 and SBRT have demonstrated safety at higher doses than prescribed in this protocol, as single agents.

If the lowest dose cohort of 1000 cGy in a single fraction is not completed with acceptable toxicity, those targets (i.e., lung or non-lung) will be excluded from the remainder of the study. If neither arm is able to be completed at the lowest SBRT dose level, the study will be terminated. If the highest dose level of 3000 cGy is reached and successfully completed, that will be the MTD for the phase IIA portion of the study. A minimum of 6 patients will be treated at the MTD in the phase Ib portion of the study.

Table 5.

Enrolled	DLT	No DLT	In follow-up	Cohort to enroll
2	0, 1	Any	Any	Enroll at same dose level
2	2	Any	Any	Enroll at lower dose level
3	0	0, 1, 2	3, 2, 1	Enroll at same dose level
3	0	3	0	Enroll at higher dose level*
3	1	0, 1, 2	2, 1, 0	Enroll at same dose level
3	≥ 2	Any	Any	Enroll at lower dose level
4	0	0, 1, 2, 3	4, 3, 2, 1	Enroll at same dose level
4	0	4	0	Enroll at higher dose level*
4	1	0, 1, 2, 3	3, 2, 1, 0	Enroll at same dose level

4	≥ 2	Any	Any	Enroll at lower dose level
5	0	0,1,2,3,4	5,4,3,2,1	Enroll at same dose level
5	0	5	0	Enroll at higher dose level*
5	1	0,1,2,3,4	4,3,2,1,0	Enroll at same dose level
5	≥ 2	Any	Any	Enroll at lower dose level
6	0	0,1,2,3,4	6,5,4,3,2	SUSPEND enrollment
6	0	5, 6	1, 0	Enroll at higher dose level**
6	1	0,1,2,3,4	5,4,3,2,1	Suspend enrollment
6	1	5	0	Enroll at higher dose level**
6	≥ 2	Any	Any	Enroll at lower dose level

*At the maximum dose level, continue current dose cohort

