**At the maximum dose level, STOP, this is the MTD

Definition of Dose Limiting Toxicity

For the purpose of determining the MTD of SBRT, a DLT will be considered to be any of the following adverse events which are probably or definitely attributable to study treatment, and which occur between the first fraction of SBRT and within 60 days of the last fraction of SBRT.

1. Any non-hematologic, non-laboratory toxicity which is grade 3 or greater and does not resolve to grade 2 or lower with supportive care within 14 days.
2. Any non-hematologic, non-laboratory toxicity which is grade 4 or greater
3. For patients in Arm A (lung targets), the development of grade 3 or greater pneumonitis that is probably or definitely attributable to either SBRT or MK-3475 within the follow-up period will be considered a DLT, regardless of whether it resolves.

54 Concomitant Medications/Vaccinations (allowed & prohibited)

Acceptable Concomitant Medications

All treatments that the investigator considers necessary for a subject's welfare may be administered at the discretion of the investigator in keeping with the community standards of medical care. All concomitant medication will be recorded on the case report form (CRF) including all prescription, over-the-counter (OTC), herbal supplements, and IV medications and fluids. If changes occur during the trial period, documentation of drug dosage, frequency, route, and date may also be included on the CRF.

All concomitant medications received within 28 days before the first dose of trial treatment and 30 days after the last dose of trial treatment should be recorded. Concomitant medications administered after 30 days after the last dose of trial treatment should be recorded for SAEs as defined in Section 7.2.

Prohibited Concomitant Medications

Subjects are prohibited from receiving the following therapies during the Screening and Treatment Phase (including retreatment for post-complete response relapse) of this trial:

- Anti-cancer systemic chemotherapy or biological therapy
- Immunotherapy not specified in this protocol
- Chemotherapy not specified in this protocol
- Investigational agents other than MK-3475
- Radiation therapy except for that specified by protocol

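### Table 5 can send patients back to a dose level that has already failed, and no written rule makes a level below the top dose the MTD

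*Combined protocol and SAP*

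**What the plan says.** Phase 1b has three levels: 10 Gy in one fraction, 30 Gy in 5 fractions (the start) and 30 Gy in 3 fractions (the top). Section 5.3 states: "A single de-escalation cohort (1000 cGy in a single fraction), and a single escalation cohort (3000 cGy in 3 fractions) will be allowed". The arms are handled independently: "Dose escalation or de-escalation will be done separately for each arm, and the MTD determined separately for each arm".

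The assignment rule is "the treatment cohort will be determined by the number of patients enrolled, the number who have experienced a DLT", together with the numbers without a DLT and still in follow-up. In Table 5:

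- No DLT in 3, 4 or 5 fully followed patients, or at most one DLT at six (with the required follow-up), means enrol at the higher level.
- Two or more DLTs means enrol at the lower level.
- The single-asterisk footnote reads "At the maximum dose level, continue current dose cohort".
- The double-asterisk footnote reads "At the maximum dose level, STOP, this is the MTD".

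The text adds "If the highest dose level of 3000 cGy is reached and successfully completed, that will be the MTD" and "A minimum of 6 patients will be treated at the MTD in the phase Ib portion of the study". For the lowest level it covers only failure, in which case those targets are excluded. Section 2.1 promises two MTDs. Section 5.3 makes an MTD the gateway to phase 2a: "Once an MTD has been determined for lung and non-lung targets, future patients with those SBRT targets will be allocated".

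**The concern.** A dose-escalation rule needs to remember which levels have failed, and it needs a definition of the MTD that can apply at any level. Table 5 has neither. Once a higher level has had two or more DLTs, a clean record at the level below still triggers the instruction to go up, because no row looks at the other level. That instruction can appear before six patients have been treated at the lower level, so it also works against the six-patient minimum at the MTD.

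Two things are at stake. One is safety: the written instruction points patients to a dose the same table has judged too toxic. The other is the phase 1b primary objective (Section 3.1). If the top dose is not tolerated, the text never says how 30 Gy in 5 fractions or 10 Gy becomes the MTD, yet phase 2a needs an MTD for that target site and uses it as the default dose.

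**Working it through.** **Stated figure.** Section 9.0 gives 12 patients treated at the MTD in phase 1b: 6 per arm × 2 arms = 12. This reproduces.

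**Completeness within a level.** Coding Table 5 over all 80 combinations of enrolled (2 to 6), DLT, no DLT and in follow-up gives exactly one action each. The fault lies only between levels.

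**Trace 1, start level fails.** 30 Gy/5 has two or more DLTs, so the row says lower. 10 Gy then has 0 DLTs in 3 fully followed patients. The row says higher, which is 30 Gy/5. The same holds at 0/4, 0/5 and at most 1/6.

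**Trace 2, top level fails.** 30 Gy/5 has 0/3, so escalate. 30 Gy/3 has two DLTs, so the row says lower, and the next patient goes to 30 Gy/5. That level is now at 4 enrolled with one in follow-up, and the row says stay. When the fourth patient clears, the row (0/4) says higher, which is 30 Gy/3. The same holds at 0/5 and at most 1/6.

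**Size.** Inputs and assumptions: a flat DLT rate p at every level, patients treated one at a time with full follow-up, starting at 30 Gy/5. The documents give no DLT rate for the combination. Of the rates below, 1% is arbitrary. The others come from Section 4.4 on lung SBRT alone, at doses higher than here: 2.6% (grade 3 pneumonitis, prospective study), 4.8% (institutional acute grade 3 or greater pneumonitis), and 6% and 14% (upper ends of the review's ranges for grade 3 or greater pneumonitis and for any grade 3 or greater toxicity).

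With q = 1 − p:

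- A, a level below the top is cleared: none of 3, or one of the first 3 and none of the next 3, so A = q³ + 3pq⁵.
- T, at most one DLT in 6 at the top: T = q⁶ + 6pq⁵.
- Conflict at 30 Gy/5 = A(1 − T). Conflict at 10 Gy = (1 − A)A.

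At p = 4.8%: q³ = 0.8628, q⁵ = 0.7820 and q⁶ = 0.7444. So A = 0.8628 + 0.1126 = 0.9754 and T = 0.7444 + 0.2252 = 0.9696. The conflicts are 0.9754 × 0.0304 = 0.0296 and 0.0246 × 0.9754 = 0.0240, total 0.0536.

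| p | at 30 Gy/5 | at 10 Gy | total | share at 10 Gy | MTD at top (A × T) |
|---|---|---|---|---|---|
| 1% | 0.0015 | 0.0012 | 0.0026 | 45% | 0.997 |
| 2.6% | 0.0094 | 0.0076 | 0.0169 | 45% | 0.983 |
| 4.8% | 0.0296 | 0.0240 | 0.0536 | 45% | 0.946 |
| 6% | 0.0442 | 0.0359 | 0.0801 | 45% | 0.919 |
| 14% | 0.1670 | 0.1387 | 0.3056 | 45% | 0.667 |

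Totals and shares are from unrounded values. These formulas read the 30 Gy/5 row as soon as the top fails. Placing one more patient there first, as in Trace 2, changes the total by less than 0.001.

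**Accrual speed.** If all six slots fill before outcomes are known, with F = 1 − T, the conflict probability is 2F(1 − F): 0.0029, 0.0187, 0.0589, 0.0876 and 0.320 at the five rates. The conflict rate is therefore not sensitive to accrual. The number of patients at the lower level is. One at a time and in the Trace 2 order, 72% (p = 14%) to 97% (p = 1%) of conflicts arise with fewer than six there; under the fast extreme none do.

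**The case against.** The strongest reply is that the text already implies the answer. Section 5.3 allows a single escalation cohort at 30 Gy in 3 fractions, which can fairly be read to bar a second entry to that level and so to close Trace 2. Targets are excluded only if 10 Gy fails, so a tolerated 10 Gy presumably carries forward. The de-escalation rows and the six-patient minimum then point to the intended dose. Section 5.3 also cites a published design, and sensible investigators would not go back to a failed dose.

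Much of this stands. The single-cohort wording is a real limit on Trace 2. It does not reach Trace 1, because 30 Gy in 5 fractions is the starting dose and not the escalation cohort, and it names no MTD. The six-patient minimum gives a size and no selection rule. Reading the maximum level as the highest level still open would solve both problems, but no text defines it so. Whether the cited paper supplies the rule cannot be judged from these documents; the protocol does not reproduce it.

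The objection to the size also has force. The anchoring rates are for lung targets, at higher doses, without MK-3475. A DLT needs probable or definite attribution within the follow-up window, and most grade 3 events also need to persist beyond 14 days. The 14% figure therefore likely overstates DLTs from SBRT alone.

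A reader might infer that a patient enrolled just after two DLTs at 30 Gy in 3 fractions goes straight back there. The table does not say that: the next patient goes to 30 Gy in 5 fractions, and when 3 patients had been cleared there, the instruction to go up returns only once 4 or more are.

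**Conclusion.** Wrong as written, minor to moderate. Table 5 has no memory of failed levels and the text has no MTD rule below the top dose. The case that no other wording rescues is the return from a cleared 10 Gy level to 30 Gy in 5 fractions. The return to 30 Gy in 3 fractions is arguably barred already.

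The size is illustrative only: about 0.3% to 8% of arms at assumed flat DLT rates of 1% to 6%, and 30% at 14%. About 45% of these conflicts are at 10 Gy. If the top dose is tolerated, the rules are complete and nothing changes.

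A reader might also infer that phase 2a could open at a dose that failed. The documents do not support this: a level with two or more DLTs always reads lower, and the double-asterisk footnote needs at most one DLT. The literal result is a loop with no declared MTD, which the investigator would have to break with a rule the protocol does not state.

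**What to change.** Add one rule to Table 5:

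*If the next higher level has already had two or more DLTs, do not re-escalate. Fill the current level to 6 patients. If at most 1 of the 6 has a DLT, this level is the MTD; otherwise de-escalate (at 10 Gy in one fraction, close the arm).*

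Every path then ends in a named MTD or a closed arm. The cost is one sentence in a short amendment. The probability that the top dose becomes the MTD is unchanged, because the rule acts only after a failure. No level exceeds 6 patients, so an arm cannot exceed 3 × 6 = 18. Under the one-at-a-time assumptions above, mean phase 1b size with the rule is 9.1 to 9.9 patients per arm at flat DLT rates of 1% to 14%. At 4.8%, the arm ends with the MTD at the top in 94.6% of cases, at 30 Gy in 5 fractions in 2.9%, at 10 Gy in 2.4%, and closed in 0.1%.

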5.6 Other Considerations

Contraception

MK-3475 may have adverse effects on a fetus in utero. Furthermore, it is not known if MK-3475 has transient adverse effects on the composition of sperm.

For this study, male subjects will be considered of non-reproductive potential if they have azoospermia (whether due to having had a vasectomy or due to any underlying medical condition).

Female subjects will be considered of non-reproductive potential if they are either:

(1) postmenopausal (defined as at least 12 months with no menses without an alternative medical cause; in women < 45 years of age a high follicle stimulating hormone (FSH) level in the postmenopausal range may be used to confirm a post-menopausal state in women not using hormonal contraception or hormonal replacement therapy. In the absence of 12 months of amenorrhea, a single FSH measurement is insufficient.);

OR

(2) have had a hysterectomy and/or bilateral oophorectomy, bilateral salpingectomy or bilateral tubal ligation/occlusion, at least 6 weeks prior to screening;

OR

(3) has a congenital or acquired condition that prevents childbearing.

Female and male subjects of reproductive potential must agree to avoid becoming pregnant or impregnating a partner, respectively, while receiving study drug and for 120 days after the last dose of study drug by complying with one of the following:

(1) practice abstinence[†] from heterosexual activity;

OR

(2) use (or have their partner use) acceptable contraception during heterosexual activity.

Acceptable methods of contraception are[‡]:

Single method (one of the following is acceptable):

- intrauterine device (IUD)
- vasectomy of a female subject's male partner
- contraceptive rod implanted into the skin

Combination method (requires use of two of the following):

- Diaphragm with spermicide (cannot be used in conjunction with cervical cap/spermicide)
- Cervical cap with spermicide (nulliparous women only)
- Contraceptive sponge (nulliparous women only)
- Male condom or female condom (cannot be used together)
- Hormonal contraceptive: oral contraceptive pill (estrogen / progestin pill or progestin-only pill), contraceptive skin patch, vaginal contraceptive ring or subcutaneous contraceptive injection

[†]Abstinence (relative to heterosexual activity) can be used as the sole method of contraception if it is consistently employed as the subject's preferred and usual lifestyle and if considered acceptable by local regulatory agencies and ERCs/IRBs. Periodic abstinence (e.g., calendar, ovulation, sympto-thermal, post-ovulation methods, etc.) and withdrawal are not acceptable methods of contraception.

[‡]If a contraceptive method listed above is restricted by local regulations/guidelines, then it does not qualify as an acceptable method of contraception for subjects participating at sites in this country/region

Subjects should be informed that taking the study medication may involve unknown risks to the fetus (unborn baby) if pregnancy were to occur during the study. In order to participate in the study, subjects of childbearing potential must adhere to the contraception requirement (described above) from the day of study drug initiation (or 14 days prior to the initiation of study drug or oral contraception) throughout the study period up to 120 days after the last dose of study drug. If there is any question that a subject will not reliably comply with the requirements for contraception, that subject should not be entered into the study.

Use in Pregnancy

If a subject inadvertently becomes pregnant while on treatment with MK-3475, the subject will immediately be removed from the study. The site will contact the subject at least monthly and document the subject's status until the pregnancy has been completed or terminated. The outcome of the pregnancy will be reported to the Sponsor and to Merck without delay and within 24 hours if the outcome is a serious adverse experience (e.g., death, abortion, congenital anomaly, or other disabling or life-threatening complication to the mother or newborn). The study investigator will make every effort to obtain permission to follow the outcome of the pregnancy and report the condition of the fetus or newborn to the Sponsor. If a male subject impregnates his female partner the study personnel at the site must be informed immediately and the pregnancy reported to the Sponsor and to Merck and followed as described above and in Section 8.

Use in Nursing Women

It is unknown whether MK-3475 is excreted in human milk. Since many drugs are excreted in human milk, and because of the potential for serious adverse reactions in the nursing infant, subjects who are breast-feeding are not eligible for enrollment.

5.7 Subject Withdrawal/Discontinuation Criteria

Subjects may withdraw consent at any time for any reason or be dropped from the trial at the discretion of the investigator should any untoward effect occur. In addition, a subject may be withdrawn by the investigator if enrollment into the trial is inappropriate, the trial plan is violated, or for administrative and/or other safety reasons. Specific details regarding discontinuation or withdrawal are provided in Section 7.

A subject must be discontinued from treatment, or removed from the study for any of the following reasons:

- The subject or legal representative (such as a parent or legal guardian) withdraws consent.
- Progression of disease during the second course of MK-3475 (as defined in section 5.2.1)
- Unacceptable adverse experiences as described in Section 5.2
- Intercurrent illness that prevents further administration of treatment
- Investigator's decision to withdraw the subject
- The subject has a confirmed positive serum pregnancy test

- Noncompliance with trial treatment or procedure requirements
- The subject is lost to follow-up
- Completed 12 months of treatment with post-SBRT MK-3475
Note: 12 months of study medication is calculated from the date of first dose of the second course. Subjects who stop MK-3475 after 12 months will be eligible for up to one year of additional study treatment if they progress after stopping study treatment
- Administrative reasons

The End of Treatment and Follow-up visit procedures are listed in Sections 6 and 7. After the end of treatment, each subject will be followed for 30 days for adverse event monitoring (serious adverse events will be collected for 90 days after the end of treatment as described in Section 8). Subjects who discontinue treatment will be followed for survival until death, withdrawal of consent, or the end of the study, whichever occurs first. Survival follow up may be a phone call only.

58 Subject Replacement Strategy

In both phases of the study, patients will be replaced if

1. They do not complete at least one fraction of SBRT.
2. They do not complete their entire course of SBRT as prescribed due to reasons other than toxicity (e.g., patient refusal, or intercurrent illness).

59 Clinical Criteria for Early Trial Termination

Early trial termination will be the result of the criteria specified below:

1. Quality or quantity of data recording is inaccurate or incomplete
2. Poor adherence to protocol and regulatory requirements
3. Incidence or severity of adverse drug reaction in this or other studies indicates a potential health hazard to subjects
4. Plans to modify or discontinue the development of the study drug

In the event of Merck decision to no longer supply study drug, ample notification will be provided so that appropriate adjustments to subject treatment can be made.

